APPENDIX 4. AESI – SUICIDAL IDEATION AND BEHAVIOR

Preferred Term
Depression suicidal
Suicidal ideation
Suicide threat
Suicidal behavior
Suicide attempt
Intentional overdose
Multiple drug overdose
Multiple drug overdose intentional
Overdose
Poisoning deliberate
Completed suicide
Intentional self-injury
Self injurious behavior
Self mutilation
Self-injurious ideation
Columbia suicide severity rating scale abnormal

APPENDIX 5. AESI – HYPOMANIA/MANIA

Affective ambivalence Affect lability Agitation Aggression
Agitation
Aggression
Anger
Bipolar disorder
Bipolar I disorder
Bipolar II disorder
Cyclothymic disorder
Delusion
Energy increased
Euphoric mood
Flight of ideas
Frustration tolerance decreased
Grandiosity
Hallucination
Hostility
Hypomania
Inappropriate affect
Irritability
Mania
Mood swings
Sexually inappropriate behavior

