I mean: having elated mood; increased energy; needing less sleep; having rapid thoughts; being full of ideas; having an increase in productivity, motivation, creativity, or impulsive behavior; phoning or working excessively or spending more money.

IF NO, CODE NO TO **C1b**: IF YES ASK:

b Are you currently feeling 'up' or 'high' or 'hyper' or full of energy? NO YES

C2 a Have you **ever** been persistently irritable, for several days, so that you had arguments or verbal or physical fights, or shouted at people outside your family? Have you or others noticed that you have been more irritable or over reacted, compared to other people, even in situations that you felt were justified? NO YES

IF NO, CODE NO TO **C2b**: IF YES ASK:

b Are you currently feeling persistently irritable? NO YES

IS **C1a** OR **C2a** CODED YES? NO YES

C3 IF **C1b** OR **C2b** = **YES**: EXPLORE THE CURRENT AND THE MOST SYMPTOMATIC **PAST** EPISODE, OTHERWISE
IF **C1b** AND **C2b** = **NO**: EXPLORE ONLY THE MOST SYMPTOMATIC **PAST** EPISODE

During the times when you felt high, full of energy, or irritable did you:

	Current Episode		Past Episode	
	NO	YES	NO	YES
a Feel that you could do things others couldn't do, or that you were an especially important person? If YES, ASK FOR EXAMPLES. <small>THE EXAMPLES ARE CONSISTENT WITH A DELUSIONAL IDEA. Current Episode  No  Yes Past Episode  No  Yes</small>	NO	YES	NO	YES
b Need less sleep (for example, feel rested after only a few hours sleep)?	NO	YES	NO	YES
c Talk too much without stopping, or so fast that people had difficulty understanding?	NO	YES	NO	YES
d Have racing thoughts?	NO	YES	NO	YES

	Current Episode		Past Episode	
e Become easily distracted so that any little interruption could distract you?	NO	YES	NO	YES
f Have a significant increase in your activity or drive, at work, at school, socially or sexually or did you become physically or mentally restless?	NO	YES	NO	YES
g Want so much to engage in pleasurable activities that you ignored the risks or consequences (for example, spending sprees, reckless driving, or sexual indiscretions)?	NO	YES	NO	YES
C3 SUMMARY: WHEN RATING CURRENT EPISODE:	NO	YES	NO	YES
IF C1b IS NO, ARE 4 OR MORE C3 ANSWERS CODED YES?				
IF C1b IS YES, ARE 3 OR MORE C3 ANSWERS CODED YES?				
WHEN RATING PAST EPISODE:				
IF C1a IS NO, ARE 4 OR MORE C3 ANSWERS CODED YES?				

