IF C1a IS YES, ARE 3 OR MORE C3 ANSWERS CODED YES?				
CODE YES ONLY IF THE ABOVE 3 OR 4 SYMPTOMS OCCURRED DURING THE SAME TIME PERIOD.				
RULE: ELATION/EXPANSIVENESS REQUIRES ONLY THREE C3 SYMPTOMS, WHILE IRRITABLE MOOD ALONE REQUIRES 4 OF THE C3 SYMPTOMS.				
C4 What is the longest time these symptoms lasted?				
a) 3 days or less				
b) 4 to 6 days				
c) 7 days or more				
C5 Were you hospitalized for these problems?	NO	YES	NO	YES
IF YES, CIRCLE YES IN MANIC EPISODE FOR THAT TIME FRAME AND GO TO C7.				
C6 Did these symptoms cause significant problems at home, at work, socially in your relationships with others, at school or in some other important way?	NO	YES	NO	YES

ARE **C3** SUMMARY AND **C5** AND **C6** CODED YES?

OR

ARE **C3** SUMMARY AND **C4c** AND **C6** CODED YES AND IS **C5** CODED NO?

SPECIFY IF THE EPISODE IS CURRENT AND / OR PAST.

NO	YES
MANIC EPISODE	
CURRENT	
PAST	

Is **C3** SUMMARY CODED **YES** AND ARE **C5** AND **C6** CODED **NO** AND IS EITHER **C4b** OR **C4c** CODED **YES**?

OR

ARE **C3** SUMMARY AND **C4b** AND **C6** CODED **YES** AND IS **C5** CODED **NO**?

SPECIFY IF THE EPISODE IS CURRENT AND / OR PAST.

IF **YES** TO CURRENT MANIC EPISODE, THEN CODE CURRENT HYPOMANIC EPISODE AS **NO**.

IF **YES** TO PAST MANIC EPISODE, THEN CODE PAST HYPOMANIC EPISODE AS **NOT EXPLORED**.

HYPOMANIC EPISODE	
CURRENT	 NO  YES
PAST	 NO  YES  NOT EXPLORED

ARE **C3** SUMMARY AND **C4a** CODED **YES** AND IS **C5** CODED **NO**?

SPECIFY IF THE EPISODE IS CURRENT AND / OR PAST.

IF **YES** TO CURRENT MANIC EPISODE OR HYPOMANIC EPISODE, THEN CODE CURRENT HYPOMANIC SYMPTOMS AS **NO**.

IF **YES** TO PAST MANIC EPISODE OR YES TO PAST HYPOMANIC EPISODE, THEN CODE PAST HYPOMANIC SYMPTOMS AS **NOT EXPLORED**.

HYPOMANIC SYMPTOMS

CURRENT **NO**
 YES

PAST **NO**
 YES
 NOT EXPLORED

C7

a) IF MANIC EPISODE IS POSITIVE FOR EITHER CURRENT OR PAST ASK:

Did you have 2 or more of these (manic) episodes lasting 7 days or more (**C4c**) in your lifetime (including the current episode if present)?

NO YES

b) IF MANIC OR HYPOMANIC EPISODE IS POSITIVE FOR EITHER CURRENT OR PAST ASK:

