3.7.3. Adverse Events of Special Interest

Adverse events of special interest (AESIs) will be summarized by Preferred Term and by prior ALKS 5461 exposure and overall during treatment period for the Safety Population / Post-discontinuation Safety Population for any TEAEs or PDEAEs of special interest. The following summaries will be created for AESI:

- TEAEs associated with abuse potential
- TEAEs associated with dependence
- PDEAEs associated with withdrawal
- TEAEs associated with suicidal ideation and behavior
- TEAEs associated with hypomania / mania
- TEAEs associated with central nervous system (CNS) depression and sedation
- TEAEs associated with respiratory depression
- TEAEs associated with orthostasis / hypotension
- TEAEs associated with hypersensitivity

- TEAEs associated with slowing of ventricular repolarization
- TEAEs associated with hepatic effects
- TEAEs associated with sexual dysfunction

TEAEs associated with abuse potential will be presented by Adhoc System Organ Class and Preferred Term, where Adhoc System Organ Class is manually classified by Alkermes medical director as 3 categories: abuse behavior, euphoria related, and non-specific.

TEAEs associated with dependence will be presented for subjects with any exposure, ≥4 weeks exposure, and <4 weeks exposure, respectively.

PDEAEs associated with withdrawal will be presented for subjects with any exposure, ≥4 weeks exposure, and <4 weeks exposure, respectively. AESIs associated with withdrawal are PDEAEs that occur from >2 to 16 days post last dose as this is the period during which physiological opioid withdrawal presents by considering half-lives of both BUP and SAM.

Supportive AE listings will be provided for each special interest group. Narratives will be provided for clinically meaningful events within each AESI group.

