APPENDIX 1. AESI – ABUSE POTENTIAL

Preferred Term	Adhoc SOC
Accidental overdose	AP_abuse behavior
Drug abuser	AP_abuse behavior
Drug diversion	AP_abuse behavior
Drug level above therapeutic	AP_abuse behavior
Drug level increased	AP_abuse behavior
Drug screen	AP_abuse behavior
Drug screen positive	AP_abuse behavior
Intentional overdose	AP_abuse behavior
Intentional product misuse	AP_abuse behavior
Intentional product use issue	AP_abuse behavior
Maternal use of illicit drugs	AP_abuse behavior
Needle track marks	AP_abuse behavior
Neonatal complications of substance abuse	AP_abuse behavior
Overdose	AP_abuse behavior
Prescription drug used without a prescription	AP_abuse behavior
Prescription form tampering	AP_abuse behavior
Product tampering	AP_abuse behavior
Substance abuse	AP_abuse behavior
Substance abuser	AP_abuse behavior
Substance use	AP_abuse behavior
Substance-induced mood disorder	AP_abuse behavior
Substance-induced psychotic disorder	AP_abuse behavior
Toxicity to various agents	AP_abuse behavior
Acute psychosis	AP_non-specific
Aggression	AP_non-specific
Cognitive disorder	AP_non-specific
Confusional state	AP_non-specific
Delirium	AP_non-specific
Delusional disorder, unspecified type	AP_non-specific
Depersonalisation/derealisation disorder	AP_non-specific
Disorientation	AP_non-specific
Dissociation	AP_non-specific
Disturbance in attention	AP_non-specific
Disturbance in social behaviour	AP_non-specific
Dizziness	AP_non-specific
Dopamine dysregulation syndrome	AP_non-specific
Emotional disorder	AP_non-specific
Flight of ideas	AP_non-specific
Medication overuse headache	AP_non-specific

Preferred Term	Adhoc SOC
Mental impairment	AP_non-specific
Mood altered	AP_non-specific
Mood swings	AP_non-specific
Narcotic bowel syndrome	AP_non-specific
Paranoia	AP_non-specific
Psychotic behaviour	AP_non-specific
Psychotic disorder	AP_non-specific
Sedation	AP_non-specific
Somnolence	AP_non-specific
Stupor	AP_non-specific
Euphoric mood	AP-euphoria related
Feeling abnormal	AP-euphoria related
Feeling drunk	AP-euphoria related
Feeling of relaxation	AP-euphoria related
Hallucination	AP-euphoria related
Hallucination, auditory	AP-euphoria related
Hallucination, gustatory	AP-euphoria related
Hallucination, mixed	AP-euphoria related
Hallucination, olfactory	AP-euphoria related
Hallucination, synaesthetic	AP-euphoria related
Hallucination, tactile	AP-euphoria related
Hallucination, visual	AP-euphoria related
Inappropriate affect	AP-euphoria related

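### The hypomania/mania AESI list omits terms for pressured speech, reduced need for sleep, distractibility and the hallucination subtypes, so TEAEs coded only to these fall outside the mania summary

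*SAP*

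**What the plan says.** SAP section 3.7.3 plans a summary of "TEAEs associated with hypomania / mania" and states how it is built: "Adverse events of special interest (AESIs) will be summarized by Preferred Term and by prior ALKS 5461 exposure and overall during treatment period". The same section promises a supportive listing for each special-interest group, and narratives for clinically meaningful events within each group. The terms for this group are in the appendix headed "APPENDIX 5. AESI – HYPOMANIA/MANIA". The section gives no other way into the group, such as a standardised query, a search of verbatim terms or a medical review.

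Protocol Appendix D reproduces the MINI. Its module C lists seven symptoms (C3a to C3g). Three of them are:
- C3b: "Need less sleep (for example, feel rested after only a few hours sleep"
- C3c: "Talk too much without stopping, or so fast that people had difficulty understanding"
- C3e: "Become easily distracted so that any little interruption could distract you"

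The counting rule follows: "ELATION/EXPANSIVENESS REQUIRES ONLY THREE C3 SYMPTOMS, WHILE IRRITABLE MOOD ALONE REQUIRES 4 OF THE C3 SYMPTOMS".

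SAP Appendix 1 (abuse potential) lists plain 'Hallucination' and seven subtypes as separate preferred terms, for example "Hallucination, auditory". Appendix 5 lists only the plain term.

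**The concern.** Emergent mania or hypomania is a named event of special interest, and bipolar disorder is an exclusion for New Subjects. Protocol Table 2 schedules the MINI at screening only and includes no mania rating scale during treatment. Coded adverse events are therefore the planned means of seeing a mood switch over 52 weeks. Protocol section 13.4 asks for all adverse events to be recorded and does not tell investigators to enter a syndrome in place of its symptoms, so coding at symptom level is realistic. If characteristic symptoms have no term on the list, some possible cases will not be identified as such in the table meant to show them.

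**Working it through.** There is no planned figure to reproduce. The check compares two lists and counts combinations.

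**1. Map the MINI to Appendix 5.** The appendix holds 23 distinct terms. A keyword search for sleep, insomnia, speech, talking, logorrhoea, attention, distraction, concentration and restlessness finds none.

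| MINI module C | Content | Appendix 5 term |
|---|---|---|
| C1 (entry) | elated or energetic | Euphoric mood, Energy increased |
| C2 (entry) | persistently irritable | Irritability, with Anger, Aggression, Hostility |
| C3a | inflated self-importance | Grandiosity |
| C3b | reduced need for sleep | none |
| C3c | excessive or rapid talking | none |
| C3d | racing thoughts | Flight of ideas |
| C3e | distractibility | none |
| C3f | increased activity, restlessness | Energy increased, Agitation |
| C3g | risky pleasure-seeking | Sexually inappropriate behavior (in part) |

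Three of the seven C3 symptoms have no term.

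**2. How often the missing symptoms enter a qualifying pattern.**
- Elated route, any 3 of 7: C(7,3) = 35 combinations. Those using only the four symptoms with some coverage number C(4,3) = 4, so 35 − 4 = 31 include at least one missing symptom. Only C(3,3) = 1 consists wholly of missing symptoms.
- Irritable-only route, any 4 of 7: C(7,4) = 35. Those without a missing symptom number C(4,4) = 1, so 34 include at least one. None consists wholly of missing symptoms, since there are only three.

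These are counts of patterns, not probabilities. Both routes also need an entry symptom (C1 or C2), and both entry symptoms have listed terms.

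**3. Where the omitted events would go.** All TEAEs appear in the tables by system organ class and preferred term and in the listings (SAP section 3.7.2). The nearest attention term, 'Disturbance in attention', and the seven hallucination subtypes are in Appendix 1 and so reach the abuse-potential table. The nearest sleep terms (Insomnia, Poor quality sleep, Terminal insomnia) are in Appendix 3, which section 3.7.3 applies to post-discontinuation events only.

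**4. Does listing a term elsewhere explain its absence here?** No. Six terms stand in both Appendix 1 and Appendix 5: Aggression, Euphoric mood, Flight of ideas, Hallucination, Inappropriate affect and Mood swings. The lists are allowed to overlap.

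**5. Weight of one event.** On the planned 1,500 subjects, one subject is 1/1,500 = 0.07 percentage points. The documents give nothing from which to estimate how many subjects would be affected.

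**The case against.** The best defence is that a real episode would usually be caught. Mania, Hypomania, Bipolar disorder, Bipolar I and II disorder and Cyclothymic disorder are all listed, as are terms for both MINI entry symptoms. An isolated symptom with neither a diagnosis nor an entry symptom does not meet the MINI rule. The MINI is also an eligibility tool here, and the SAP does not adopt it as the definition of the outcome. Sleep trouble, restlessness and poor concentration are depressive symptoms in MINI module A, so loosely chosen additions would bring background depression into a mania table.

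Most of this stands, and it rules out several stronger readings:
- A reader might infer that these events can never reach the mania result. They can, through a reported diagnosis or a listed mood term, and they remain in the general tables in any case.
- A reader might infer that counting irritability, anger or aggression is an error. Irritability is itself a MINI entry symptom. Rows are by preferred term, so core and non-specific terms can already be told apart, and splitting the table is a matter of layout.
- A reader might put a multiple on the under-count. Any such figure would only restate assumed case numbers.
- A reader might infer from the spelling 'behavior' in Appendices 4 and 5, against 'behaviour' in Appendix 1, that three terms would return nothing. The matching method is left to separate programming specifications (SAP section 8), so this is a check to make and not a demonstrated failure.

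The defence does not explain why a list that already includes many single symptoms leaves out these three, or why it counts one hallucination term and not its subtypes.

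**Conclusion.** The point holds in a limited form. Three of the seven MINI C3 symptoms, and seven hallucination subtypes that the SAP itself names elsewhere, are outside the hypomania/mania group. A TEAE coded only to one of them, with no listed diagnosis or mood term reported for that subject, is left out of the group's summary, listing and narrative pool. It is not lost from the trial's adverse event reporting. The number of subjects affected is unknown and may be small.

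This rests on three assumptions: that Appendix 5 is complete as read (its opening rows are disordered in the text available); that MedDRA 19.0 does not code such verbatim reports to a term already listed, which the documents cannot settle; and that the MINI serves as a benchmark of content and not as the SAP's definition. The hallucination point does not depend on the MINI. It follows from comparing Appendix 1 with Appendix 5.

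**What to change.** Before database lock, amend SAP Appendix 5 as follows:
1. Add the seven hallucination subtypes already in Appendix 1.
2. Add the matching MedDRA 19.0 preferred terms for pressured or excessive speech and for reduced need for sleep, chosen from the dictionary by the coding group and kept distinct from insomnia.
3. For distractibility, either add 'Disturbance in attention' or record that it is left out because it overlaps with depression.

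Separately, ask programming to confirm that terms are matched by code or in the dictionary spelling, so that the 'behavior' entries in Appendices 4 and 5 are found.

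The cost is an appendix edit and a re-run of one AESI table and its listing. The downside is a few more non-diagnostic events in that table. Settling the terms before the data are seen avoids any question about how they were chosen.

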APPENDIX 6. AESI – CNS DEPRESSION AND SEDATION

Preferred Term
Apathy
Asthenia
Bradyphrenia
Decreased activity
Decreased interest
Depressed level of consciousness
Fatigue
Hypersomnia
Hypersomnia related to another mental condition
Hypokinesia neonatal
Hyporesponsive to stimuli
Hypotonic-hyporesponsive episode
Lethargy
Listless
Loss of consciousness
Neonatal oversedation
Prostration
Psychomotor retardation
Sedation
Sense of oppression
Sleep disorder due to general medical condition, hypersomnia type
Sluggishness
Somnolence
Somnolence neonatal
Sopor
Unresponsive to stimuli

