3.7.2. Adverse Events

Adverse events will be coded by System Organ Class and Preferred Term using the Medical Dictionary for Regulatory Activities MedDRA version 19.0. The verbatim term will be included in the AE listings. An AE will be considered as a treatment emergent adverse event (TEAE) if it starts or worsens (if present at baseline) on or after the baseline during treatment period. An AE will be considered as a PDEAE if it starts or worsens during the Post-discontinuation Safety Period which is after the last dose date plus 1 day. For the determination of TEAEs during the treatment period, AEs with the greatest severity before the baseline will be used as the benchmark for the comparison of the AEs occurring during the treatment period. For PDEAEs, the greatest severity before or on the last dose date plus 1 day will be used as the benchmark for the comparison of the AEs occurring during the Post-discontinuation Safety Period.

All AEs will be listed by subject. TEAEs / PDEAEs, deaths, serious adverse events (SAEs), AEs leading to study discontinuation will be included in the summary tables. Summary tables will be provided by prior ALKS 5461 exposure and overall for the Safety Population. For AEs leading to study discontinuation or deaths, the AEs will be summarized in the period in which the discontinuation or death occurred. Drug related TEAEs include those scored as definitely related, probably related, and possibly related by the investigator.

The following summary tables will be produced for the treatment period / Post-discontinuation Safety Period by prior ALKS 5461 exposure and overall for the Safety Population:

- Overview AE summary tables (TEAEs / PDEAEs)
- TEAEs / PDEAEs by System Organ Class and Preferred Term
- TEAEs / PDEAEs by Preferred Term in decreasing frequency
- TEAEs / PDEAEs experienced by ≥5% of subjects (in any group) by Preferred Term
- TEAEs / PDEAEs by System Organ Class, Preferred Term, and Severity
- Drug-related TEAEs by System Organ Class and Preferred Term
- SAEs (fatal and non-fatal) by System Organ Class and Preferred Term
- SAEs (fatal and non-fatal) by Preferred Term in decreasing frequency
- AEs leading to study discontinuation by System Organ Class and Preferred Term
- AEs leading to study discontinuation by Preferred Term in decreasing frequency
- TEAEs by System Organ Class, Preferred Term, and Duration of Exposure
- TEAEs by Preferred Term in decreasing frequency and Duration of Exposure

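### The CNS-depression and sedation term list (SAP Appendix 6) omits Stupor, although it lists the neighbouring terms and Appendix 1 uses Stupor as a preferred term

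*SAP*

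**What the plan says.** SAP 3.7.3 states that "Adverse events of special interest (AESIs) will be summarized by Preferred Term", split by prior ALKS 5461 exposure and overall. It names twelve groups, one of which is CNS depression and sedation, analysed as TEAEs. It adds that "Supportive AE listings will be provided for each special interest group", and it promises narratives for clinically meaningful events in each group. The terms are set out in Appendices 1 to 12, one per group. The SAP does not say how the lists were drawn up.

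All adverse events are coded in one dictionary, "MedDRA version 19.0" (SAP 3.7.2).

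Appendix 6 holds the CNS-depression and sedation terms. Its last entry is "Unresponsive to stimuli", and the entry before that is Sopor.

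Appendix 1 holds the abuse-potential terms in three categories. Stupor is the last entry in the non-specific category, after Sedation and Somnolence.

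**The concern.** No other membership rule is given, so the appendix list alone decides which events enter each AESI summary. Stupor describes a marked reduction in consciousness, and Appendix 6 already takes in the terms closest to it. Its absence looks like an oversight.

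The study's objective is long-term safety and tolerability, and the product contains a partial opioid agonist. A summary of CNS depression that counts fatigue and apathy but not stupor leaves out a term from the severe end of its own range. The error can run in one direction only: the group is undercounted, never overcounted.

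**Working it through.** There is no sample-size, power or error-rate figure to reproduce. The check compares the lists.

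**Appendix 6, counted term by term: 26 terms.** They run in unbroken alphabetical order from Apathy to Unresponsive to stimuli. Stupor would fall between Sopor and Unresponsive to stimuli. It is not there, and there is no visible gap.

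**Appendix 1, counted by category:** 23 abuse behaviour + 26 non-specific + 14 euphoria related = 63 terms. Stupor is one of the 26.

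| Term | Appendix 1 | Appendix 6 |
|---|---|---|
| Sedation | yes | yes |
| Somnolence | yes | yes |
| Stupor | yes | **no** |
| Sopor | no | yes |
| Depressed level of consciousness | no | yes |
| Loss of consciousness | no | yes |
| Unresponsive to stimuli | no | yes |

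Four possible reasons for leaving Stupor out can be tested against the text.

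1. *It is not an available preferred term.* Appendix 1 uses it as one, and the same dictionary version applies to all events.
2. *A term may sit in one list only.* The SAP does not work that way. Of the 63 Appendix 1 terms, these also appear in another AESI list:
   - Appendix 4: 2 (for example "Intentional overdose")
   - Appendix 5: 6 (for example "Euphoric mood")
   - Appendix 6: 2 (Sedation, Somnolence)
   - Appendix 8: 1 (Dizziness)

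   The total is 2 + 6 + 2 + 1 = 11. This shows only that repetition is allowed. It does not measure the effect of the omission.
3. *The list was kept narrow.* It includes Apathy, Asthenia, Decreased interest, Fatigue and Sense of oppression. It also includes three neonatal terms (Hypokinesia neonatal, Neonatal oversedation, Somnolence neonatal) in a study of adults.
4. *The term is too severe for the list.* Loss of consciousness and Unresponsive to stimuli are included.

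None of the four explains the absence.

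**Where a Stupor event would still be seen.**
- The abuse-potential AESI summary, by preferred term under the non-specific heading, with its listing, and a narrative if the event is clinically meaningful (SAP 3.7.3).
- "TEAEs / PDEAEs by System Organ Class and Preferred Term", and the tables by severity and by duration of exposure (SAP 3.7.2).
- The drug-related, SAE or discontinuation tables, where the event qualifies (SAP 3.7.2).
- The by-subject listing: "All AEs will be listed by subject".

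**Where it would not be seen.** The CNS-depression and sedation AESI summary and its listing. A subject who also has a listed term, such as Somnolence, remains in that summary, but the Stupor row is missing from it.

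**The case against.** The strongest reply is that no rule is broken. The SAP sets no completeness criterion for the lists and does not require a term in one list to be carried into another. Choosing AESI terms is a medical judgement. Repetition is also the exception: 63 − 11 = 52 of the Appendix 1 terms are in no other AESI list, and only 2 of the 63 are in Appendix 6. The list is selective elsewhere too. Syncope is in Appendices 3 and 8 but not in Appendix 6, and Confusional state and Disorientation are not carried over from Appendix 1.

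Much of this stands. The case for adding Stupor rests on its closeness in meaning to Sopor and the other listed consciousness terms, not on a breach of the SAP. But the reply does not say why Stupor should be out when Sopor, on one side of it, and Fatigue, on the other, are in.

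A reader might infer that stupor events would disappear from safety reporting, or that Appendix 6 feeds the only table from which sedation can be judged. The documents support neither reading. Stupor is already an AESI term under abuse potential, where it is shown by preferred term beside Sedation and Somnolence, and the general tables and listing carry it as well.

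A row lost when the table was converted from PDF cannot be excluded from the text alone. Appendix 6 shows no sign of damage, and a look at the SAP page settles it.

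**Conclusion.** The omission is real and its effect is small. One preferred term is missing beside 26 listed. A subject whose only relevant TEAE is coded to Stupor is absent from one AESI summary and its listing, and is present everywhere else the SAP reports adverse events.

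The conclusion rests on two assumptions: that Stupor belongs with the consciousness terms already in Appendix 6, and that the list in the SAP text is complete as shown. The documents give no count of stupor events, and the mock tables are in a separate document (SAP section 9), so the number of subjects affected and any change in a printed percentage are unknown. It would be wrong to infer that the sedation rate is materially understated. The study is descriptive, and no test or threshold depends on the AESI count. This is a cheap improvement, at the lowest level of severity.

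**What to change.** Add Stupor to Appendix 6, between Sopor and Unresponsive to stimuli, and keep it in Appendix 1. Appendix 6 then has 26 + 1 = 27 terms. Protocol 14.2 places finalization of the SAP before database lock, which is the natural time to do this. If the SAP is already signed, a short documented addendum, carried into the programming specifications, is enough.

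The cost is one row in one list. Sample size, data collection and error rates do not change. Stupor will be counted in two AESI tables, as Sedation and Somnolence already are, so counts must not be added across AESI tables; a footnote can say so. A stupor event with another cause may enter the CNS-depression table and need medical review, as with any term on the list.
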